### 1.5.2.2 Pasireotide LAR in PLD patients

Preclinical studies in the PCK rat (a recessive model of polycystic kidney and liver disease) showed that the SST analog octreotide reduces cAMP levels in kidney and bile ducts and slows the progression of hepato-renal cystogenesis. We previously completed a double-blinded, randomized, placebo-controlled clinical trial (NCT00426153) using OctLAR over 1 year in forty-two patients with severe polycystic liver disease (PLD), due to autosomal dominant polycystic liver disease (ADPLD) or autosomal dominant polycystic kidney disease (ADPKD). By magnetic resonance imaging, the mean liver volume decreased from 5907 to 5557 ml (4.95 ± 7.00%) in the octreotide group (n = 28) compared with 5374 to 5361 ml (0.92 ± 7.00%) in the placebo group (n = 14). This difference (mean 4.95 *versus* 0.92%) was significant (P= 0.045). The self-reported SF-36 quality of life form demonstrated a significant improvement in perception of body pain and physical function in octreotide-treated patients. Moreover, three separate prospective clinical trials have now shown similar positive effects of SST analogs in ADPLD and ADPKD. A few other published reports relating to the use of SST analogs further substantiate these observations. All of these studies were limited by small numbers of enrolled patients with a

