### 10.2 Statistical methods

Demographics and laboratory data will be plotted (e.g. box plots) and summarized by treatment group. Frequency distributions will be used to describe categorical values and basic summary statistics (mean, standard deviation, median, and inter-quartile range) used to describe continuous values. All tests will be two-sided with alpha level 0.05. For quantitative endpoints (e.g. change in kidney and liver volumes, renal function, and SF-36 scales) the two-group independent samples t-test will be used to test for an effect of treatment. Should the assumptions of normality and equality of variances be untenable, we will consider a data transformation or use of the Wilcoxon rank sum test. Both point estimates (mean) and 95% confidence intervals will be used to summarize treatment effects. For qualitative endpoints (e.g. presence or absence of response) we will compare treatment groups using the chi-square or Fisher's exact test as appropriate.

**Efficacy (Liver & kidney):** The primary analysis of treatment efficacy will follow intent-to-treat principles, attempting to include all randomized patients. For the primary endpoint (change in

liver volume) we will not be able to include anyone without a 12 month MRI (kidney volumes will be handled in the same way). For the “response” endpoints, those without a 12 month MRI will be included in the analysis as non-responders. Secondary analysis – Efficacy (QOL): We will have up to 5 longitudinal assessments of QOL for each patient. Repeated measures analysis of variance will be used to compare mean QOL profiles over time between treatment groups. Also, within patient rates of change or slopes in QOL measures will be estimated (using simple linear regression) and compared between groups using the two-sample t-test.

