**Secondary analysis–Kidney volume will be measured as part of the efficacy analysis:**

AEs (both patient and event counts) will be tabulated by organ system (neuro, GI, etc.), individually, by severity and, for each severity, by investigator-assessed relationship to study drug. Fisher’s exact test will be used to compare treatment groups regarding adverse events. Patients who received at least one dose of the randomized study drug will be included.

**Statistical power:** The primary endpoint is one year percentage change in liver volume. Prior data in untreated patients suggest a growth rate (SD) of 5(±3) % per year. We have planned a 2:1 randomization in order to allow as many patients as possible to receive SOM230. The goal is to detect up to a 7.3% percentage point decrease in the mean cyst growth using SOM230 LAR® Depot. With **15 placebo and 30 SOM230** patients, the study will have 80% power (alpha=.05, two-sided) to detect a 7 percentage point difference. To allow for dropouts (1 placebo and 2 SOM230 patients without endpoint data); the study will randomize 16 placebo and 32 SOM230 patients. For any quantitative endpoint the study is powered to detect a difference in treatment means of at least one standard deviation. Secondary endpoints include comparison of responder rates (based on liver and renal growth) and adverse event rates between the two groups. With 16 and 32 patients, a true placebo response (or adverse event rate) of 8 % (1 of 13) vs. 30, 40, or 50% for SOM230 can be detected with 45%, 70%, and 88% power, respectively.

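### The Wilcoxon fallback in Section 10.2 does not correct unequal variances at 2:1 allocation and does not test the reported mean difference; prespecify Welch's test

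*Combined protocol and SAP*

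**What the plan says.** Section 10.2 sets the general rule that "All tests will be two-sided with alpha level 0.05". For quantitative endpoints, including change in liver volume, "the two-group independent samples t-test will be used to test for an effect of treatment". The fallback, for the case that normality and equal variances prove untenable, reads: "we will consider a data transformation or use of the Wilcoxon rank sum test". On reporting, "Both point estimates (mean) and 95% confidence intervals will be used to summarize treatment effects".

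The power paragraph at the end of the same section states that "The primary endpoint is one year percentage change in liver volume" and plans on 15 placebo and 30 SOM230 patients with endpoint data.

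Section 10.2 does not describe the t-test as the equal-variance form, but it lists equality of variances among the test's assumptions. Neither a Welch test nor robust standard errors appear anywhere. The plan gives no diagnostic, no threshold, no named transformation and no rule for which of the two alternatives applies.

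**The concern.** The plan recognises unequal variances as a threat and names a remedy, so the question is whether the remedy works. With a 2:1 split, the pooled standard error gives most weight to the larger arm's variance, whereas the true variance of the mean difference depends more on the smaller arm's. The t-test is therefore too strict if the active arm is more variable and too lenient if placebo is. The Wilcoxon test is affected in the same direction, to a lesser degree.

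There is also a mismatch of target. If the p-value came from a Wilcoxon test and the interval from a difference in means, the two could disagree, and the plan does not say which one governs.

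The year-1 result decides more than the publication. Section 6.10 says that the open-label extension will be terminated if no efficacy is found in the first-year analysis.

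**Working it through.** **Inputs.** 30 active and 15 placebo patients, two-sided alpha 0.05, target difference 7 points (Section 10.2). SDs of percent change in liver volume: 7.00 on octreotide and 7.00 on placebo in the prior trial; 7.58 treated and 8.35 untreated in the pooled analysis (both Section 1.5.2.2); 3 in untreated patients (power paragraph). The pairs 5/10, 7.7/11.55 and 11.55/7.7 are assumptions, chosen to show SD ratios of 2 and 1.5. The pair 7/3 combines two sources and is also treated as an assumption.

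**The plan's own figure.** The t-test has 43 degrees of freedom and noncentrality 7 / (SD × √(1/30 + 1/15)) = 7 / (0.3162 × SD). At SD 3 this is 7.38 and power exceeds 99.99%. The stated 80% needs a common SD of about 7.7 (noncentrality 2.87, power 80.2%). The calculation therefore appears to assume an SD near 7.7 in both arms, and 7.7 serves below as the equal-variance reference.

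**Why the t-test drifts.** True variance of the mean difference: V = s_A²/30 + s_P²/15. Expected value of the pooled estimate: P = [(29 s_A² + 14 s_P²)/43] × 0.1. The ratio √(P/V) shows how far the pooled standard error is off.

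- 7.00/7.00: V = 4.90, P = 4.90, ratio 1.00.
- 7.58/8.35: V = 1.92 + 4.65 = 6.56, P = 6.15, ratio 0.97.
- 7/3: V = 1.63 + 0.60 = 2.23, P = 3.60, ratio 1.27 (standard error 27% too large).
- 5/10: V = 0.83 + 6.67 = 7.50, P = 4.94, ratio 0.81 (19% too small).

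**Type I error.** Simulation of 100,000 trials per row with normal data (Monte Carlo standard error about 0.07 points at 5%). The two-stage rule uses Wilcoxon if a Brown-Forsythe test gives p < 0.05 and the t-test otherwise. That trigger is an assumption, because the plan gives none.

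| Active / placebo SD | t-test | Wilcoxon | Two-stage | Welch |
|---|---|---|---|---|
| Equal | 5.0% | 4.9% | 5.0% | 5.0% |
| 7.58 / 8.35 | 5.8% | 5.4% | 5.7% | 5.0% |
| 11.55 / 7.7 | 2.6% | 3.5% | 2.8% | 5.0% |
| 7.7 / 11.55 | 8.7% | 7.0% | 7.6% | 5.1% |
| 7 / 3 | 1.5% | 3.1% | 2.7% | 5.0% |
| 5 / 10 | 11.2% | 8.5% | 8.7% | 5.0% |

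Repeat runs differed by a few tenths of a point at most. HC3 standard errors on 43 degrees of freedom, without covariates, stayed between 4.5% and 5.4% over the scenarios run. HC2 reached 6.1% at active 3 / placebo 7.

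**Power, t-test against Welch.**

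- 7 points, SD 7.7 in both arms: 80.0% against 79.0%.
- 7 points, 7.58/8.35: 78.0% against 74.6%.
- 7 points, 7/3: about 98% against 99.5%.
- 4.03 points (the prior trial's 4.95 − 0.92), 7/3: 56% against 75%, with Wilcoxon at 62%.

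**Skew.** With lognormal errors (sigma 0.5) and active 3 / placebo 7, the level for equal means was 7.0% for Welch, 13.3% for the t-test and 16.9% for Wilcoxon.

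**Transformation.** This was not simulated, because none is named. A transformation equalises variances only if variance tracks the mean, and percent change takes negative values, so a plain log of it is not available.

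**The case against.** The strongest objection is that the problem may not arise. A reader might infer from the documents that the arms will differ sharply, by setting "Prior data in untreated patients suggest a growth rate (SD) of 5(±3) % per year" against "4.95 ± 7.00%) in the octreotide group". The documents do not support that reading. The sentence that gives 7.00 on octreotide also gives 7.00 on placebo. The pooled analysis gives 7.58 against 8.35, a ratio of 1.10 in the opposite direction. The SD of 3 comes from separate external references, one of which is titled as a study of early ADPKD, while this trial enrols severe PLD. The two within-programme comparisons suggest similar variances, and there the t-test is at or near its level. This part of the objection stands and limits the size of the point.

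A reader might also infer that choosing the test after seeing the data adds error of its own. That is not shown for this plan. Section 10.2 switches on failed assumptions; it does not take the smaller of two p-values. The assumed two-stage rule gives 5.0% at equal SDs and 5.7% at 7.58/8.35, no worse than the t-test alone. Where placebo is much more variable, it reduces the error in part.

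It is also fair to say that Welch's gain is small at the planned 7-point difference, that it occurs only when the active arm is more variable, and that Welch is not exact under strong skew.

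None of this makes the fallback work. If its own trigger occurs, the Wilcoxon test remains mis-sized and still addresses a different quantity from the one reported.

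**Conclusion.** The point holds in a limited form. When variances differ at 30:15, the Wilcoxon part of the stated remedy leaves type I error at about 3% (7/3) or 8.5% (5/10), where Welch gives 5%. It also separates the p-value from the reported mean difference and interval. No verdict is possible on the transformation part.

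On the documents' same-programme SDs the consequence is small: nominal at 7.00/7.00, and about 5.6 to 5.9% for the t-test at 7.58/8.35, against 5.3 to 5.4% for Wilcoxon and 5% for Welch. Material distortion requires an SD ratio of about 1.5 or more, which is an assumption. The figures rest on normal data unless stated otherwise. The case for changing the plan is that the remedy fails in the situation it is meant for and that a better one costs little.

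**What to change.** In Section 10.2, name one primary test for percent change in liver volume at month 12. Use Welch's t-test, or a linear model adjusted for baseline liver volume and the ADPKD/ADPLD stratum with HC3 standard errors. Take the p-value and the 95% confidence interval from that same analysis. Remove the open choice between a transformation and the Wilcoxon test, and keep Wilcoxon as a labelled sensitivity analysis. If the model is chosen, specify HC3 rather than HC2; the covariate-adjusted version was not simulated here.

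The change is one of wording only. For a 7-point difference it costs about 1 point of power if the SDs are equal (80% to 79% at SD 7.7) and about 3 points at 7.58/8.35 (78% to 75%). Part of the latter loss reflects the t-test's inflated level.

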## **4 Study design**

This study will be conducted over 3 years as a randomized, double-blind control, clinical trial through year 1, followed by an open-label extension phase for the subsequent 2 years. Screening and randomization visits will take place at Mayo Clinic and patients will then be followed by Mayo Clinic for three years. We will monitor the patients with blood and urine tests on days 22, 29, 50, 57 and 89 and then at Months 6, 9, 12, 15, 18, 24, 27, 30, 33 and 36. Follow up visits will occur at one and three months post last dose of study drug. For patients who received placebo during year one, the labs on days 22, 29, 50, 27 and 85 will be repeated as these are safety labs. All patients will be required to undergo MRI or CT scan imaging at the baseline, 12 month (end

of year 1) and 36 month (end of year 3) visits to fulfill the primary study endpoints. Safety monitoring with ECG, Hemoglobin A1C, liver function and glucose testing will be performed locally at the study sub-sites and monitored centrally by study staff at Mayo Clinic.

Patients will be recruited during visits to the Department of Nephrology and Hypertension

Patients who had participated in previous studies will also be contacted as long as they meet all eligibility criteria. We will also recruit through [clinicaltrials.gov](http://clinicaltrials.gov) ( <http://clinicaltrials.gov> ), Mayo Clinic Trials website ( <http://clinicaltrials.mayo.edu/> ) and PKD foundation clinical trials ( <http://www.pkdcure.org/Research/ClinicalTrials/ActiveRecruiting.aspx> ) listed on the web . Patients who contact the study coordinator will be given information regarding the study and participation. The study coordinator will screen those interested and proceed with the study design for all patients who would like to participate.

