## 6.5 Pasireotide LAR dose adjustment

We will use the oncology dosing (including NETs) as already described above, pasireotide LAR at 60 mg every 28 days being the recommended starting dose for oncological indications. If tolerability issues occur, the treatment dose may be reduced to pasireotide LAR at 40 mg with next scheduled injection. Patients requiring a dose reduction can return to the higher dose once the tolerability issue is resolved. However, patients not able to tolerate the minimum pasireotide LAR dose of 20 mg are recommended to be discontinued from study.

All dose changes must be recorded on the Dosage Administration Record CRF. Table 7 outlines the dose reduction steps for pasireotide.

Emergency un-blinding will be done at the discretion of the Principal Investigator [REDACTED] in cases where she feels it is necessary for the safety of the patient.

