**Renal****Serum creatinine**

< 2 x ULN	Maintain dose level
2-3 x ULN	Omit dose until resolved to ≤ Grade 1, then 
 
• If resolved ≤ 7 days, then maintain dose level
 
• If resolved > 7 days, then ↓ 1 dose level
 

Grade 3 (> 3.0 - 6.0 x ULN)	Omit dose and discontinue patient from study treatment
Grade 4 (> 6.0 x ULN)	Omit dose and discontinue patient from study treatment

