**AST or ALT**

Grade 1 (> ULN - 2.5 x ULN)	Maintain dose level
Grade 2 (> 2.5 - 5.0 x ULN)	Maintain dose level
Grade 3 (> 5.0 and ≤ 8x ULN)	For ALT or AST > 5x ULN and ≤ 8x ULN: 
 
• Study medication should be temporarily interrupted & liver chemistry monitored every 3-4days until resolution or return to baseline.
 
• If resolution or return to baseline does not occur after 2 weeks, the patient should be discontinued.
 
• If ALT or AST returns to less than 5x ULN, study drug can be resumed and patient can continue study per protocol
 
• If ALT or AST rises above 5x ULN anytime after study drug is resumed, then study drug should be discontinued immediately.
 

Grade 4 (> 20.0 x ULN)	Omit dose and discontinue patient from study treatment

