## 6.8 Study drug discontinuation

Study drug must be discontinued and the subject withdrawn from the trial if the investigator determines that continuing would result in significant safety risk for that subject. The following circumstances require study drug discontinuation:

Pregnancy

The occurrence of an adverse event or of a clinically significant laboratory change or abnormality that, in the judgment of the investigator, warrants discontinuation of treatment.

Subjects who have fasting plasma glucose > 240 mg/dL confirmed by repeat measurement

Any CTC grade 3 or higher abnormalities in hematology or chemistry parameters judged clinically significant by the Investigator

Any confirmed QTcF > 500 ms or confirmed increase of QTcF > 60 ms from baseline

ALT or AST > 3x ULN and Total Bilirubin  $\geq$  2 x ULN and ALP > 2 x ULN

ALT or AST > 5x ULN and  $\leq$  8 x ULN persistent for more than 2 weeks

ALT or AST > 8 x ULN

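### The primary mean comparison drops patients without a 12-month scan and has no sensitivity analysis, and the protocol conflicts on whether early stoppers are scanned

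*Combined protocol and SAP*

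**What the plan says.** **Analysis.** Section 10.2 states: "The primary analysis of treatment efficacy will follow intent-to-treat principles". For change in liver volume it then adds: "we will not be able to include anyone without a 12 month MRI". For the response endpoints, "those without a 12 month MRI will be included in the analysis as non-responders". The planned test is an unadjusted two-sample t-test, with a transformation or the Wilcoxon test as fallback. No imputation or other sensitivity analysis of the mean change is described.

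**Imaging.** Section 4 says: "All patients will be required to undergo MRI or CT scan imaging at the baseline, 12 month", and again at month 36.

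**Stopping drug.**
- Section 6.8, when the investigator judges that continuing carries a significant safety risk: "Study drug must be discontinued and the subject withdrawn from the trial".
- Sections 6.5 and 6.6: patients who cannot tolerate the lowest dose "are recommended to be discontinued from study".
- Table 7, for example the higher serum creatinine grades: "Omit dose and discontinue patient from study treatment".
- Section 6.9 asks patients who withdraw early to attend an Early Termination Visit. Table 8 gives that visit the same column as month 36.
- Section 4.2 continues follow-up until 3 months after the last injection.

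**Expected loss.** The power paragraph of Section 10.2 allows for 1 placebo and 2 SOM230 patients without endpoint data, out of 16 and 32. Section 6.10 does not expect discontinuation above 15%.

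**The concern.** The primary mean describes randomised patients who have a 12-month scan, which is not the same set as all randomised patients. The gap matters only if scans are missing for reasons related to treatment or outcome, and the plan leaves room for that. The triggers in Section 6.8 include confirmed high fasting glucose and QTcF prolongation, and Section 1.5 reports effects of pasireotide on both. Among carcinoid patients on the LAR form, 18/42 had grade 3 or 4 glucose elevation. If a safety stop also ends imaging, scans could be lost more often on SOM230.

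Much of that loss would be avoidable, because Section 4 already schedules the scan. A month-12 scan that is not taken cannot be recovered later. For scans that are lost, no planned analysis of the same endpoint shows how far the result depends on them.

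**Working it through.** **1. Is a year-1 stopper scanned at month 12?**

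| Place | Reading |
|---|---|
| Section 4 | Yes, all patients (MRI or CT) |
| Section 6.8 | No, if withdrawal from the trial ends visits |
| Sections 6.5, 6.6 | No, if leaving the study ends visits |
| Table 7, creatinine | Only treatment stops; imaging not affected |
| Section 4.2 | No, if the last injection was before about month 9 (9 + 3 = 12) |
| Section 6.9, Table 8 | Early Termination Visit, probably with a scan; the column alignment of Table 8 is unclear in the text available here |

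An early-termination scan is not a 12-month MRI, so Section 10.2 read literally still excludes that patient. Section 10.2 also names only MRI, although Sections 4 and 7.4.1.1 allow CT.

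**2. The plan's power figure, to obtain a standard error.** Inputs from Section 10.2: 15 placebo and 30 SOM230, 7 points, two-sided 0.05, 80% power. By noncentral t with 43 df, 80% power needs d = 0.906, so SD = 7 / 0.906 = 7.72. The growth SD of 3 printed there does not reproduce the figure: it gives power above 99.9%. That is a separate matter, and nothing here uses it. The SD of 7.00 reported for the earlier octreotide trial in Section 1.5.2.2 gives 87.1%.

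SE = SD × sqrt(1/15 + 1/30):
- SD 7.72: 2.44
- SD 7.00: 2.21

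At 15% loss in both arms (13.6 and 27.2 expected): 7.72 × sqrt(1/13.6 + 1/27.2) = about 2.56.

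**3. Shift in the mean difference.** Let fS and fP be the fractions unscanned on SOM230 and placebo, k the share of the 7-point effect that unscanned SOM230 patients keep, and g the extra growth of unscanned placebo patients over scanned ones.

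Overstatement = 7 × fS × (1 − k) − fP × g

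The illustration takes k = 0 and g = 0:
- Planned loss: 7 × 2/32 = 0.44 points; 0.44 / 2.44 = 0.18 SE (0.20 SE with SD 7.00).
- 15% of scans missing: 7 × 0.15 = 1.05 points; 1.05 / 2.56 = 0.41 SE.

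Other assumed values, with equal fractional loss in both arms:

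| k | g | Planned loss (2/32, 1/16) | 15% loss |
|---|---|---|---|
| 1 | +7 | −0.44 | −1.05 |
| 0.5 | +3.5 | 0.00 | 0.00 |
| 0 | 0 | +0.44 | +1.05 |
| 0 | −7 | +0.88 | +2.10 |

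The sign and size depend on k and g, which the documents do not give. The table is not a bound: k below 0 is possible, since Section 6.9 permits withdrawal for disease progression.

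**4. Precision.** For an ANCOVA with two covariates and 41 df, using d / sqrt(1 − R²), power is 79.9% at R² = 0, 83.9% at 0.10 and 87.9% at 0.20. The R² values are assumed; the documents give none.

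**The case against.** The plan is open about the exclusion and budgets for it: three losses in 48 are allowed for. The responder endpoint comes from the same liver-volume measurement and counts missing scans as failures. An Early Termination Visit exists. Imaging is done at one center, so variation between sites in reading the rule is not a concern. At planned loss the illustrated shift is under a fifth of a standard error.

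Much of this stands, and it keeps the point modest. But the responder analysis is on a dichotomised endpoint and cannot show how far the mean moves. An allowance for lost sample size does not address selective loss.

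The conflict should also not be overcounted. Table 7 is about dosing, so its ALT/AST row, "If resolution or return to baseline does not occur after 2 weeks, the patient should be discontinued", most naturally means off drug. The real tension is between Section 4 on one side and Sections 6.8 and 4.2 on the other, with Sections 6.5 and 6.6 adding to it.

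Three stronger inferences are tempting, and the documents do not support them:
- **That the exclusion favors SOM230.** Section 6.9 also allows withdrawal for lack of efficacy or disease progression, which could remove fast-growing placebo patients. Section 1.5.1 reports few hyperglycemia discontinuations on the SQ form.
- **That 15% is the expected scan loss.** In Section 6.10 it is a ceiling on discontinuation. It equals scan loss only if no stopper is scanned, which is the unresolved point.
- **That the 1/42 discontinuation in the team's octreotide trial is a year-1 scan-loss rate.** Section 6.10 places it after one year, and Section 1.5.2.2 prints 12-month volumes under group sizes of 28 and 14, which is all 42.

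**Conclusion.** The point holds as a matter that should be fixed, not as a fatal flaw. Three facts rest on the text alone: the primary mean uses only patients with a 12-month scan, it has no missing-data sensitivity analysis, and the protocol gives conflicting instructions on imaging after an early stop.

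The consequence is less certain. If unscanned SOM230 patients have the placebo mean, the overstatement is 0.44 points at planned loss and 1.05 points if 15% of scans were missing, against a 7-point effect. These figures rest on an SD of 7.72 back-solved from the stated power and on assumed outcomes of unscanned patients. Other assumptions give smaller, larger or opposite shifts, so no direction of bias is claimed.

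The missing covariate adjustment is a separate question of precision. It has no bearing on the missing scans.

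**What to change.** 1. **Imaging follow-up.** Reconcile Sections 4, 4.2, 6.5, 6.6, 6.8, 6.9 and Table 8 on imaging only, leaving every stopping criterion unchanged. Patients who stop drug in year 1 and still consent have the already scheduled month-12 MRI or CT and are analysed as randomised. Cost: protocol wording, a return visit for some patients off drug, and possibly two scans for an early stopper.

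2. **Missing scans.** Prespecify one sensitivity analysis of the mean percent change. It gives unscanned SOM230 patients placebo-arm growth and then varies the assumed growth of unscanned patients in both arms. State whether an early-termination scan, or a CT, can serve as the 12-month measurement. Describe the main analysis set as all randomised patients with a 12-month scan. Cost: analysis-plan wording and a small amount of programming.

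3. **Precision, separately.** Replace the t-test on percent change with ANCOVA on treatment, ADPLD/ADPKD stratum and baseline liver volume, all already collected. Cost: two degrees of freedom. Power is 79.9% instead of 80% if the covariates explain nothing, and 83.9% to 87.9% if they explain an assumed 10% to 20% of the variance.

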### **7.4 Efficacy**

#### **7.4.1 Liver & total kidney volume, hepatic cyst volume, renal cyst volume**

##### **7.4.1.1 Primary outcome**

The primary outcome is the percent change in liver volume as assessed by MR at baseline, 12 and 36 months follow-up. Patients will also be classified as “responders” if their liver volume decreases, does not change, or increases by <2% over the 12 month study period. The MR techniques for imaging and interpretation of volumetric measurements established in the CRISP study will be employed in the present study, as early results from the CRISP study indicate that this MR protocol will provide an effective means for longitudinal evaluation of liver and kidney volume and of cyst volume and is much more sensitive in detecting cholelithiasis when compared to CT, because CT cannot differentiate between the density of bile in the gallbladder and the more common, non-calcified gallstones. T-2 weighted images on MR can easily demonstrate stark contrast between the bright fluid (bile) in the gallbladder from the dark gallstones which do not have any signal intensity on MRI. The MR Procedure comprises of the following (30 minutes):

1. Since no gadolinium will be used in this study, patients will not have an angiocatheter placed at the time of their MRI. (See exception for patients undergoing CT below.)
2. ECG pads will be placed over the chest. If ECG gating is not available or functioning, it may be replaced with a peripheral pulse gating. Hair may need to be shaved off to place the leads.
3. Subjects will be placed supine on the MR table with their arms to their sides.
4. A phased-array surface coil will be positioned with its center over the liver.
5. Scout scan to locate the scan range of the entire liver.
6. The field-of-view (FOV) should be kept as small as possible (30-35 cm) without producing wrap-around artifacts.
7. Obtain breath-hold coronal Regular T2 scan (SSFSE/HASTE with fat sat) with 9mm fixed slice thickness, usually achievable in a single breath-hold.
8. Obtain breath-hold coronal Regular T2 scan (SSFSE/HASTE with fat sat) of the liver with adjusted slice thickness, 3-9 mm, i.e. the slice thickness best attainable with a single breath-hold (the adjusted slice thickness may not remain the same in a follow-up MR scan if there is a change in the subject's breath-hold capacity or liver size).
9. Repeat the scan over the kidneys with the same slice thickness.

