The measurements of liver, kidney and cyst volumes will be performed without knowledge of group assignment using the technology developed for the CRISP study. Liver and kidney vol-

umes will be measured in T1-weighted images with a stereology method and calculated from the set of contiguous images by summing the products of the area measurements and slice thickness. A region-based threshold method will be used to calculate cyst volumes.

In patients who are unable to undergo MRI (e.g. due to claustrophobia) a CT scan of the liver and kidneys will be substituted. CT scans will be performed with or without contrast, depending of renal function. If estimated GFR is greater than 60 iodinated IV contrast will be employed. If renal function is less than 60mls/min, no iodinated contrast will be used. A peripheral IV cannula will be inserted for patients requiring IV contrast and removed immediately after the scan is completed.

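### Section 10.2 ties the primary analysis set and responder scoring to a 12-month MRI, while other sections accept CT for the same endpoint

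*Combined protocol and SAP*

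**What the plan says.** Section 10.2 sets the aim: "The primary analysis of treatment efficacy will follow intent-to-treat principles, attempting to include all randomized patients". For change in liver volume it then says "we will not be able to include anyone without a 12 month MRI", with kidney volume handled likewise. For the response endpoints, "those without a 12 month MRI will be included in the analysis as non-responders". CT is not mentioned in 10.2.

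Section 7.4.1.1 defines the endpoint in MR terms: "The primary outcome is the percent change in liver volume as assessed by MR at baseline, 12 and 36 months follow-up". It classes a patient as a responder if liver volume falls, is unchanged, or rises by less than 2% over 12 months. The same section later says: "In patients who are unable to undergo MRI (e.g. due to claustrophobia) a CT scan of the liver and kidneys will be substituted".

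Section 4 treats the two modalities as alternatives: "All patients will be required to undergo MRI or CT scan imaging at the baseline, 12 month" and 36-month "visits to fulfill the primary study endpoints". The imaging row of Table 8 shows CT in brackets beside MRI. The severity criterion in 5.2.1 accepts either modality, and 7.4.1.2 takes liver volumes from either.

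**The concern.** A patient who cannot have MRI and is scanned by CT has followed the protocol and has a measured volume at month 12. Under the wording of 10.2 that patient has no 12-month MRI. The literal result is exclusion from the primary liver and kidney volume analyses and a score of non-responder, even if the liver shrank. Nothing is missing in such a case, so the usual reason for counting a patient as a failure does not apply.

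One analyst working from 10.2 could exclude CT patients while another working from section 4 includes them. The primary analysis set of a 48-patient trial should not rest on that choice. The year-1 efficacy result also decides whether the open-label extension continues (6.10). Section 6.3 gives allocation access to the biostatistician who does the analysis or database lock, so an open question about inclusion could be settled with the allocation known.

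**Working it through.** **Passages side by side, for a patient with CT at baseline and month 12**

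| Place | Modality named | Consequence |
|---|---|---|
| 10.2, volume endpoints | MRI | excluded if literal |
| 10.2, response | MRI | non-responder if literal |
| 7.4.1.1, endpoint definition | MR | unclear |
| 7.4.1.1, substitution text | CT replaces MRI | volume counts |
| Section 4 | MRI or CT | serves the primary endpoints |
| Table 8 | MRI, CT in brackets | scan accepted |
| 7.4.1.2, liver | MRI/CT | volume counts |

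If the CT volume fell, 7.4.1.1 makes this patient a responder and 10.2 makes the same patient a non-responder.

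**How many patients.** The documents give no CT rate. Assuming 2% to 10% of 48 gives 0.96 to 4.8, or about 1 to 5 patients. The allowance for patients without endpoint data is 48 − 45 = 3 (1 placebo, 2 SOM230).

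**Response rate.** One CT responder scored as a failure moves the rate by 1/16 = 6.25 points in placebo or 1/32 = 3.1 points in SOM230. If a fraction f of each arm has CT only, both rates and their difference shrink by (1 − f). Take 8% versus 40%, one of the plan's scenarios:
- f = 0: difference 32.0 points, pooled-z power 66.5% (the plan states 70%)
- f = 5%: 32.0 × 0.95 = 30.4 points, power 62.6%
- f = 10%: 32.0 × 0.90 = 28.8 points, power 58.7%

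**Primary power, the plan's figure first.** Section 10.2 states 80% power for a 7-point difference with 15 placebo and 30 SOM230 patients, two-sided alpha 0.05. I used the two-sample t-test with df = n1 + n2 − 2 and noncentrality 7 / (SD × √(1/n1 + 1/n2)).
- With SD 3%, the only SD in that paragraph, power exceeds 99.9%, so 80% does not reproduce.
- With SD 7.58%, from the pooled octreotide data in 1.5.2.2, power is 81.4%.
- Exactly 80% needs SD 7.72, which is used below. Noncentrality is then 7 / (7.72 × √0.1) = 2.87.

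The next table shows power when CT patients are lost in addition to the planned dropouts.

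| Lost (placebo + SOM230) | Evaluable | Noncentrality | Power |
|---|---|---|---|
| 0 + 0 | 15/30 | 2.87 | 80.0% |
| 0 + 1 | 15/29 | 2.85 | 79.5% |
| 1 + 2 | 14/28 | 2.77 | 77.1% |
| 2 + 4 | 13/26 | 2.67 | 73.8% |

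Three CT exclusions with no other dropout would use up the allowance and leave power at 80%.

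**The case against.** The strongest reply is that MRI in 10.2 is shorthand for the 12-month volumetric scan. Section 4 ties MRI or CT to the primary endpoints. The substitution text stands inside the primary outcome section. Section 10.2 speaks of being unable to include patients, which describes missing data, and its dropout allowance is for patients without endpoint data. A patient with a CT volume fits neither description. The documents also use MRI loosely elsewhere: 7.4.1.2 names both modalities for liver and only MRI for kidney. All this stands. A reader might infer that CT patients will certainly be dropped. The documents do not support that, since no sentence excludes CT volumes and several point the other way.

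The shorthand reading is still not secure. Several passages name both modalities where both are meant, footnote 10 of Table 8 treats them as different procedures, and both section 2 and the endpoint definition in 7.4.1.1 name only MR.

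The effect is also likely to be small. Section 8 provides a standing sedative order for claustrophobic patients before MRI, which addresses the only reason for CT that the plan gives as an example. The 6.3-point placebo shift needs a placebo CT patient who responds, and at the plan's 8% rate only 16 × 0.08 = 1.28 placebo responders are expected in all.

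Finally, 7.4.1.1 gives no CT volumetry method, so the documents do not establish that the two modalities are interchangeable. Simply admitting CT would let in patients with MRI at one visit and CT at the other, with no rule for them. The fix has to cover that.

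**Conclusion.** The point holds as an unresolved conflict between a stated analysis rule and the design text. Followed to the letter, 10.2 discards an observed volume, contradicts the responder definition in 7.4.1.1 and works against the plan's intent-to-treat aim. Whether it would be applied that way cannot be settled from the documents.

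The probable effect is small. Power goes from 80% to about 77% if three evaluable patients are lost beyond the dropout allowance, and one misclassified responder costs 3.1 or 6.3 points of response rate. These figures rest on assumed CT counts, on equal CT fractions in the two arms for the dilution figures, and on an SD of 7.72 back-solved from the stated power. The inconsistency itself rests on wording alone and depends on none of them.

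**What to change.** 1. In both sentences of 10.2, make inclusion depend on a 12-month liver (or kidney) volume from MRI, or from CT where substituted. Score as non-responders only patients with no 12-month volume.
2. In 7.4.1.1, change the endpoint definition so that it names CT as the substitute.
3. Before the year-1 unblinding, state that a patient's baseline and month-12 volumes should come from the same modality, and add a sensitivity analysis that excludes any mixed MRI/CT pairs.

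If MRI only is intended, the plan should say so, justify it and change section 4 to match.

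The cost is a few lines of text and one extra analysis run, with no change to visits, sample size or data collection.
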